9.1 Specification of Safety Parameters

Unanticipated problems (UPs) will be recorded in the data collection system (REDCap) and must be reported to the IRB and NIDCR in accordance with Duke IRB-defined timeline for reporting policy. An Adverse Event must be reported to the IRB if it: (i) is more likely than not related to study activities; and (ii) represents a new risk; and (iii) is unanticipated. In addition, an expected event that is occurring at a frequency or intensity greater than originally anticipated must be reported to the IRB.

UPs include incidents, experiences, and outcomes that are not adverse events, as well as a subset of adverse events. This study will follow Duke IRB policy for reporting other events to the IRB.

All serious adverse events (SAEs) that are also determined to be UPs will be reported to NIDCR and the IRB concurrently, for assessment by the NIDCR Medical Monitor.

Determining whether a particular adverse event is unexpected by virtue of an unexpectedly higher frequency can only be done through an analysis of appropriate data on all subjects enrolled in the research. If the investigator determines that an adverse event is not an unanticipated problem, but the NIDCR Medical Monitor subsequently determines that the adverse event does represent an unanticipated problem (for example, due to an unexpectedly higher frequency of the event), the NIDCR Medical Monitor will report this determination to the investigator, and such reports must be promptly submitted by the investigator to the IRB.

9.1.1 *Unanticipated Problems*

The Office for Human Research Protections (OHRP) considers unanticipated problems involving risks to subjects or others to include, in general, any incident, experience, or outcome that meets **all** of the following criteria:

- unexpected in terms of nature, severity, or frequency given (a) the research procedures that are described in the protocol-related documents, such as the IRB-approved research protocol and informed consent document; and (b) the characteristics of the subject population being studied;
- related or possibly related to participation in the research (“possibly related” means there is a reasonable possibility that the incident, experience, or outcome may have been caused by the procedures involved in the research); and
- suggests that the research places subjects or others at a greater risk of harm (including physical, psychological, economic, or social harm) than was previously known or recognized.

9.1.2 *Adverse Events*

An adverse event is any untoward or unfavorable medical occurrence in a human subject, including any symptom temporally associated with the subject’s participation in the research, whether or not considered related to the subject’s participation in the research.

9.1.3 *Serious Adverse Events*

A serious adverse event (SAE) is one that meets one or more of the following criteria:

- Results in death
- Is life-threatening (places the subject at immediate risk of death from the event as it occurred)
- Results in inpatient hospitalization or prolongation of existing hospitalization
- Results in a persistent or significant disability or incapacity
- An important medical event that may not result in death, be life threatening, or require hospitalization may be considered an SAE when, based upon appropriate medical judgment, the event may jeopardize the subject and may require medical or surgical intervention to prevent one of the outcomes listed in this definition.

9.2 Time Period and Frequency for Event Assessment and Follow-Up

The PI and/or study team will record all events occurring any time after informed consent is obtained until the subject leaves the clinic. Subjects will only be allowed to leave the clinic once resolution of the event or patient stabilization occurs. This is adequate for the following reasons: 1) trained physicians skilled with endoscopic examinations are present to conduct the procedure and observe patients, 2) incidence of adverse events is rare, and 3) direct visualization of the placement of the scope will occur, thus preventing adverse events.

9.3 Characteristics of an Adverse Event

Each event will be recorded on an appropriate case report form that includes assessment of the characteristics defined below. These characteristics, along with the frequency of an event's occurrence, will be considered in determining if the event is a UP.

9.3.1 Relationship to Study Intervention

To assess relationship of an event to study intervention the following guidelines are used:

1. Related (Possible, Probable, Definite)
 - a. The event is known to occur with the study intervention, and/or
 - b. There is a temporal relationship between the intervention and event onset and/or
 - c. The event abates when the intervention is discontinued, and/or
 - d. The event reappears upon a re-challenge with the intervention.
2. Not Related (Unlikely, Not Related)
 - a. There is no temporal relationship between the intervention and event onset, and/or
 - b. An alternate etiology has been established.

9.3.2 Expectedness

The Study PI and/or study-appointed, clinically/medically responsible individual will determine whether an AE is expected or unexpected. An AE will be considered unexpected if the nature, severity, or frequency of the event is not consistent with the risk information previously described for the intervention.

9.3.3 Severity of Event

The following scale will be used to grade adverse events:

1. Mild: no intervention required
2. Moderate: minimal, local, or non-invasive intervention indicated
3. Severe: significant symptoms requiring invasive intervention; subject seeks medical attention

9.4 Reporting Procedures

9.4.1 Unanticipated Problem Reporting

Incidents or events that meet the OHRP criteria for unanticipated problems require the creation and completion of an unanticipated problem report form. OHRP recommends that investigators include the following information when reporting an adverse event, or any other incident, experience, or outcome as an unanticipated problem to the IRB:

- appropriate identifying information for the research protocol, such as the title, investigator's name, and the IRB project number;
- a detailed description of the adverse event, incident, experience, or outcome;
- an explanation of the basis for determining that the adverse event, incident, experience, or outcome represents an unanticipated problem;
- a description of any changes to the protocol or other corrective actions that have been taken or are proposed in response to the unanticipated problem.

To satisfy the requirement for prompt reporting, unanticipated problems will be reported using the following timeline:

- Immediately (within 24 hours) upon learning of an unanticipated study-related death, study personnel will notify the IRB via phone or e-mail by providing a brief summary of the event. Then, within 1 week (five business days), study personnel will send to the IRB a Safety Event submission in the eIRB.
- All unanticipated problems should be reported to appropriate institutional officials (as required by an institution's written reporting procedures), the supporting agency head (or designee), and OHRP within one month of the IRB's receipt of the report of the problem from the investigator.

All unanticipated problems will be reported to NIDCR concurrently with reporting to the IRB. These reports will be made to NIDCR's centralized reporting system via the CROMS contractor. Additional reporting instructions can be found in the MOP.

9.4.2 Serious Adverse Event Reporting

The study's clinically responsible individual will complete a Serious Adverse Event Form and submit via fax or email within the following timelines:

- For a reportable serious adverse event, study personnel will notify the IRB within five business days of the investigator becoming aware of the event. Study personnel will send a Safety Event submission in the eIRB.
- For any other problem or event requiring prompt reporting to the IRB, within ten business days of the investigator becoming aware of the event, study personnel will send to the IRB a Safety Event submission in the eIRB.

All SAEs will be followed until resolution or stabilization.

9.5 Halting Rules

Subsequent review of serious, unexpected, and related AEs by the Medical Monitor, Data and Safety Monitoring Board (DSMB), IRB, the sponsor(s), or relevant local regulatory authorities may also result in suspension of further study interventions/administration of study product at a site. The study sponsor(s) retain the authority to suspend additional enrollment and study interventions/administration of study product for the entire study, as applicable.

Examples of findings that might trigger a safety review are the number of SAEs overall, the number of occurrences of a particular type of SAE, severe AEs/reactions, or increased frequency of events.

10 STUDY OVERSIGHT

[name], [name] and [name] will have monthly meetings to assess progress and FNS feedback from end users.

The Advisory Board for this project is comprised of leaders in biomedical engineering, global health, and device development. The role of the advisory board will include advising regarding optimizing the prototype within the specified time period of 3 months. [name] (PI, Duke University), and [name] (Vivo Surgical) will have formal meetings with the advisory board twice per year.

In addition to the PI's responsibility for oversight, study oversight will be under the direction of the Specialized Technology and Devices for Head and Neck Cancers (STAND) Data and Safety Monitoring Board (DSMB), who is composed of members with expertise in Head and Neck Squamous Cell Carcinoma and imaging, bioethics/health policy, practice-based research, and biostatistics. The DSMB will meet regularly, at an interval to be determined, to assess safety and efficacy data, study progress, and data integrity for the study. Per instructions given by the DSMB, safety reports will include the grades of adverse events and a summary of changes to the protocol, if there are any. The first DSMB safety report will be submitted three months following the start of the study. If safety concerns arise, more frequent meetings may be held. The DSMB will operate under the rules of an NIDCR-approved charter that will be approved at the organizational meeting of the DSMB. At this time, most data elements that the DSMB needs to assess will be clearly defined. The DSMB will provide recommendations to the NIDCR.

11 CLINICAL SITE MONITORING

The sponsor-investigator or principal investigator (PI), and Duke Cancer Institute (DCI), through the PRMS and PRMC, will monitor this clinical research study. For internal review, the sponsor-investigator or PI will continuously monitor and tabulate adverse events. The study team will make reports to the Duke University Hospital System (DUHS) Institutional Review Board (IRB). If an unexpected frequency of Grade III or IV events occur, depending on their nature, action appropriate to the nature and frequency of these adverse events (AE) will be taken. This may require a protocol amendment or potentially study closure. The study sponsor-investigator or PI will also continuously monitor study conduct, data, and safety to ensure:

- Interim analyses occur as scheduled.
- Stopping rules for toxicity and/or response are met.
- Risk/benefit ratio is not altered to subject detriment.
- Appropriate internal AE and outcomes monitoring is performed.
- Over-accrual does not occur.
- Under-accrual is addressed with appropriate amendments or actions.
- Data are being appropriately collected in a reasonably timely manner.

PRMS protocol review begins with the PRMC. PRMC new protocol reviews focus on scientific relevance, study design, biostatistical input adequacy, protocol prioritization, feasibility of study completion within a reasonable time frame and trial risk assessment. The sponsor-investigator or PI will abide by PRMC risk level assessment. PRMC also conducts annual scientific progress reviews on protocols open to enrollment and focuses on protocol prioritization, accrual, and scientific progress. The PRMC conducts reviews at the time of IRB annual renewals and maintains documentation in iRIS.

During the initial PRMC approval, the PRMC determines the monitoring risk level and frequency which will be commensurate with the type and level of intervention, phase, endpoints, degree of risk, size, and protocol complexity. The DCI monitoring team will conduct formal, independent monitoring according to the risk level and the PRMC monitoring plan until the study is closed to enrollment or subjects are no longer receiving study drug or other interventions that are more than minimal risk.

The DCI has determined this study to be “moderate risk/complexity”. Moderate Risk is defined as “Behavioral intervention, complex observational or sample/tissue or blood collection studies deemed more than minimal risk. These studies require a physical intervention with a participant”.

Per the DCI’s Data and Safety Monitoring Plan (DSMP), moderate risk studies undergo the following: A minimum of 10% of records to be reviewed every 6 months. Review may be more frequent based on findings in initial study review, enrollment, or at the request of the DCI Safety Oversight Committee or School of Medicine Clinical Quality Management Program.

Findings from monitoring visits, unexpected frequency of serious and/or unexpected toxicities, or other concerns may prompt additional monitoring. DUHS and DCI Leadership, PRMC, DCI Safety Oversight Committee (SOC), a sponsor, an investigator, or the IRB may also request additional monitoring visits.

The DCI monitoring team reviews informed consent adequacy, eligible patient enrollment, protocol-specified procedures and treatment implementation, data collection adequacy, and adverse event monitoring and reporting appropriateness. The DCI monitoring team presents final monitoring reports to the DCI SOC highlighting safety concerns and unresolved issues. The SOC, at a convened meeting, assigns an overall rating of satisfactory, marginal, or unsatisfactory to reflect the overall data quality, regulatory, consent, eligibility, study conduct, and AE reporting. Corrective action plans (CAPs) are developed, implemented, and evaluated as indicated. The SOC will notify the sponsor-investigator or PI and DUHS IRB when significant safety concerns are identified.

The SOC in conjunction with the DCI monitoring team conducts data and safety monitoring for DUHS sponsor-investigator or PI Phase I and II, therapeutic interventional oncology studies that do not have an independent Data Safety Monitoring Board (DSMB). These reviews occur at a minimum annually and possibly more frequently based on risk level. The SOC safety reviews include safety, data accuracy, enrollment status, stopping rules if applicable, accrual, toxicities, reference literature, and interim analyses as the sponsor-investigator provides. The SOC, at a convened meeting, assigns a “satisfactory” rating when adequate accrual with lack of excessive toxicity is present.

Clinical site monitoring is conducted to ensure that the rights of human subjects are protected, that the study is implemented in accordance with the protocol and/or other operating procedures, and that the quality and integrity of study data and data collection methods are maintained. In addition, monitoring for this study will be performed by NIDCR's Clinical Research Operations and Management Support (CROMS) contractor. The monitor will evaluate study processes and documentation based on NIDCR standards and the International Conference on Harmonisation (ICH), E6: Good Clinical Practice guidelines (GCP).

Details of documented in a Clinical Monitoring Plan (CMP) developed by the CROMS contractor, in collaboration with the NIDCR Office of Clinical Trials and Operations Management (OCTOM) and the NIDCR Program Official. The CMP will specify the frequency of monitoring, monitoring procedures, the level of clinical site monitoring activities (e.g., the percentage of subject data to be reviewed), and the distribution of monitoring reports. Some monitoring activities may be performed remotely, while others will take place at the study site(s). Staff from the CROMS contractor will conduct monitoring activities and provide reports of the findings and associated action items in accordance with the details described in the CMP. Documentation of monitoring activities and findings will be provided to the site study team, the study PIs, OCTOM,

and the NIDCR. The NIDCR reserves the right to conduct independent audits as necessary.

12 STATISTICAL CONSIDERATIONS

12.1 Study Hypotheses

The study hypothesis is that a low cost FNS can be non-inferior to the SOC scope in terms of ease of use, image quality, and perceived pain.

12.2 Sample Size Considerations

Aim 1 is aimed at optimizing the FNS for its optimal functioning as explained in the recruitment described above.

Fixing alpha at 0.05, power at 80%, a sample size of 37 produces a two-sided 95% confidence interval with a width equal to 0.2 when the sample proportion of success is 0.9. The lower and upper confidence interval for this success rate of 0.9. is 0.76 and 0.96 respectively (PASS 16, 2018). Hence at the end of testing on 37 subjects, if the proportion who answer good outcomes as described in scenario 1 is between 0.76 and 0.96, phase one of the study is a success.

Power Analysis and Sample Size Software (2018). NCSS, LLC. Kaysville, Utah, USA, ncss.com/software/pass).

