12.3 Final Analysis Plan

Statistical Analysis – Aim 1: Optimization Phase.

1. Outcome 1 (Primary): The primary outcome is ease of use comparison between the FNS to the SOC scope (score of 1 – 5, with 1 being very hard and 5 being very easy).
2. Outcome 2 (Secondary): Quality of the image (image quality score range 1-5, with 1 being poor and 5 being excellent).
3. Outcome 3 (Secondary): Perceived pain between the FNS to the SOC scope (pain score range of 1 – 3, with 1 being much more and 3 being much less).

Scenario 1:

Success of this first phase 1 (Aim 1) after evaluating 37 subjects is defined as - (1) at least 90% response of ease of use of second scope compared to first score to range from same to excellent (3 to 5); and (2) 90% responding to better video quality of second scope compared to first (score ranging from same to excellent (3 to 5); and (3) 90% responding to pain score of same or much less (2 or 3); In short, this phase is a success if 90% respond to same to excellent/much less on all 3 of the outcomes.

[figure not shown]
Scenario 2: If the rate is between 50 to < 90% for any three outcomes in a sample from 37, then the plan is to proceed recruiting more subjects until 50 are recruited. At 50 subjects, if in scenario 1 then phase 1 is a success and phase 1 is complete; if not, fine tune the prototype.

Scenario 3: If the rate is < 50% for any one of the 3 outcomes described above, then the plan is to proceed to fine tuning the prototype.

The primary outcome of ease of use of scope as reported by the physicians, will be examined between the two different scopes, at the simplest level, using paired Z-test if the scores (or transformed scores) are normally distributed or by using Wilcoxon test if the scores are non-normal.

The analysis for secondary outcomes of the change in the quality of the videos and pain will each be examined using paired Z-test, if the change (or transformed scores) is normally distributed or by Wilcoxon test if the change is non-normal. Assumptions of each of these tests will be examined. The significance of each of the outcomes will be examined at alpha = 0.05. The reliability of this instrument (using intra-class-correlation (ICC)) will be first assessed by using the data from the first 50 subjects. If ICC is < 0.9, we will include training component and necessary adjustment for the physicians.

See diagram below

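### Section 12.2 claims 80% power for a sample size that comes only from a confidence-interval width, and the chance of meeting the success rule is not given for either of two conflicting rules

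*Combined protocol and SAP*

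**What the plan says.** Section 12.2 states: "Fixing alpha at 0.05, power at 80%, a sample size of 37 produces a two-sided 95% confidence interval with a width equal to 0.2", and adds that this applies "when the sample proportion of success is 0.9". It then gives the limits: "The lower and upper confidence interval for this success rate of 0.9. is 0.76 and 0.96 respectively". From these it draws a success rule for that sample size: "if the proportion who answer good outcomes as described in scenario 1 is between 0.76 and 0.96, phase one of the study is a success".

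Section 12.3 sets a different rule. Scenario 1, also assessed at 37 subjects, requires "at least 90% response of ease of use of second scope" and 90% on video quality and on pain as well; all three must be met. Scenario 2 continues recruitment to 50 when rates lie from 50% to below 90%, and applies Scenario 1 again at 50. Scenario 3 sends the prototype to fine-tuning if any outcome is below 50%.

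Section 12.1 states a non-inferiority hypothesis for the three outcomes, without a margin or a reference proportion.

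**The concern.** Power is the probability that a stated test or decision rule succeeds under a stated alternative. Section 12.2 attaches 80% power to an interval-width calculation, which has neither a test nor an alternative. The plan therefore claims a property that its calculation does not have, and it nowhere gives the probability that a prototype of a given quality meets the success criterion.

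That probability matters because the criterion decides whether the optimization phase is complete, recruitment continues to 50, or the prototype is reworked. Two success rules apply at the same 37 subjects and they behave very differently, so no single probability can be given until one of them is chosen.

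**Working it through.** **Inputs.** From 12.2: n = 37, proportion 0.9, two-sided 95% interval, width 0.2, limits 0.76 and 0.96, and the success band 0.76 to 0.96. From 12.3: at least 90% on each of three outcomes at 37, extension to 50, and fine-tuning if any outcome is below 50%. Assumed, because the documents do not give them: the true rate p, taken as equal on all three outcomes, and the correlation between outcomes, taken from independence to perfect positive correlation.

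**1. Reproduce the plan's figure.** Wilson interval with z = 1.96, so z² = 3.8415:

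- centre = (0.9 + 3.8415/74) / (1 + 3.8415/37) = 0.9519/1.1038 = 0.8624
- half-width = (1.96/1.1038) × √(0.9 × 0.1/37 + 3.8415/(4 × 37²)) = 1.7756 × √(0.002432 + 0.000702) = 0.0994
- limits 0.763 and 0.962, width 0.199

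At n = 36 the width is 0.2016, so 37 is the smallest n with width at most 0.2. The plan's n and limits are reproduced. No power term enters.

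**2. Section 12.3 rule at 37.** 0.9 × 37 = 33.3; 33/37 = 89.2% fails and 34/37 = 91.9% passes. At p = 0.90, the binomial probabilities of 34, 35, 36 and 37 favourable responses are 0.2161, 0.1667, 0.0834 and 0.0203, which sum to 0.486.

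- One outcome, or three perfectly correlated: 48.6%
- Three independent outcomes: 0.4864³ = 11.5%

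**3. Section 12.3 rule by 50.** Here at least 45/50 is needed (0.9 × 50 = 45). I assume that any cohort that misses Scenario 1 at 37 but has no outcome below 50% (at least 19/37) is extended. Let A = P(at least 34/37), B = P(at least 45/50, with at least 19/37 at the first look) and C = P(at least 34/37 and at least 45/50). Then:

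- one outcome, or perfect correlation: A + B − C
- three independent outcomes: A³ + B³ − C³

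At p = 0.90, A = 0.4864, B = 0.6161 and C = 0.4513. One outcome gives 0.651. Three independent outcomes give 0.1151 + 0.2339 − 0.0919 = 0.257.

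The same formulas at the other rates:

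| True rate | A | B | C | At 37: one outcome | At 37: three independent | By 50: one outcome | By 50: three independent |
|---|---|---|---|---|---|---|---|
| 0.85 | 0.1736 | 0.2194 | 0.1349 | 17% | 0.5% | 26% | 1.3% |
| 0.90 | 0.4864 | 0.6161 | 0.4513 | 49% | 12% | 65% | 26% |
| 0.95 | 0.8881 | 0.9622 | 0.8830 | 89% | 70% | 97% | 90% |
| 0.97 | 0.9757 | 0.9963 | 0.9751 | 98% | 93% | 99.7% | 99% |

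The one-outcome columns also serve for three perfectly correlated outcomes.

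**4. Section 12.2 band at 37.** Proportions from 0.76 to 0.96 are 29 to 35 of 37; 28/37 = 75.7% is too low and 36/37 = 97.3% too high. I apply the band to each outcome.

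- p = 0.90: P(28 or fewer) = 0.0093 and P(36 or 37) = 0.0834 + 0.0203 = 0.1036, so 1 − 0.0093 − 0.1036 = 0.887. Three independent: 0.887³ = 0.698.
- p = 0.95: P(36 or 37) = 0.2919 + 0.1499 = 0.4418, and P(28 or fewer) is negligible, so 0.558. Three independent: 0.558³ = 0.174.

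Under the band, the better prototype is less likely to succeed.

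**The case against.** The strongest reply is that the sample size is not wrong. It meets its stated precision, 12.2 promises no pass probability, and it calls 0.9 a sample proportion, not an expected true rate. Any rule that requires the observed rate to reach a threshold succeeds roughly half the time when the truth sits at that threshold; this follows from where the bar is set and is no slip in the calculation. All of that stands. It leaves the 80% with nothing to refer to.

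Two stronger readings are tempting. The first is that a prototype performing at 90% will usually be sent to redesign after 37 subjects, or that a miss will be taken as a poor device. The documents do not support this. Missing 90% at 37 leads to further recruitment under Scenario 2. Fine-tuning at that look needs an outcome below 50%, which is practically impossible at a true rate of 0.90. The plan also treats a miss as a reason to refine the prototype.

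The second is that the decision at 37 has a 12% to 49% chance of success without qualification. That holds for Scenario 1 only. Under the band in 12.2 the range is about 70% to 89%, which straddles 80%. The plan does not derive its 80% from that rule either.

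Two limits on the figures also stand. The Scenario 2 wording about three outcomes can be read in more than one way. Video quality is collected as a separate 1 to 5 rating for each scope but scored in Scenario 1 as if it were one comparative rating, so its success rate is not fully defined.

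**Conclusion.** The point holds in this form: the 80% power statement in 12.2 has no content, because n = 37 rests on interval width alone. At an assumed true rate of 0.90 on each outcome, the Section 12.3 rule succeeds with probability about 12% to 49% at 37 and about 26% to 65% by 50, so it does not reach 80% even with the extension and perfect correlation. The conflicting rule in 12.2 gives about 70% to 89% at 0.90 and falls to 17% to 56% at 0.95.

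These ranges rest on a common true rate, on correlation between independence and perfect positive correlation, and, for the by-50 figures, on extending every cohort with no outcome below 50%. The lower ends are not floors, since negative correlation would take them lower. A reader might infer that 37 subjects are too few. The documents do not support that: the number is right for the stated precision, and no power target tied to a test is defined against which it could fall short.

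**What to change.** 1. In 12.2, delete the 80% power phrase and say that 37 was chosen to give a 95% Wilson interval of width 0.2 for each outcome at a proportion of 0.9.
2. Reconcile the 0.76 to 0.96 success sentence in 12.2 with Scenario 1 in 12.3 so that one success rule remains. Removing the power phrase alone would leave two contradictory criteria at 37.
3. Report the retained rule's probability of success at 37 and by 50 for true rates 0.85, 0.90, 0.95 and 0.97, for one outcome and for all three, with the correlation and the extension condition stated as assumptions. If Scenario 1 is kept, the table in the working can serve.

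The cost is wording, a small table and a less favourable stated figure. No extra subjects are needed.
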